8.1.2 Adverse Event Severity

The severity of AEs and SAEs will be graded according to the Toxicity Grading Scale for Healthy Adult and Adolescent Volunteers Enrolled in Preventive Vaccine Clinical Trials, Sept 2007.

Any AE not listed in this scale will be graded as follows:

- Mild: The event is easily tolerated by the participant and does not affect the participant's usual daily activities
- Moderate: The event causes the participant more discomfort and interrupts the participant's usual daily activities
- Severe: The event is incapacitating and causes considerable interference with the participant's usual daily activities

If the event is an SAE, then all applicable seriousness criteria must be indicated (criteria listed in Section 7.1.4).

8.1.3 Adverse Event Relationship to Study Medication

Reactogenic and solicited events with onset within 7 days of injection of ARCT-021 will be regarded as related to the last study vaccine injected.

For other events, the event's relationship to the study vaccine is characterized as shown below. For the purposes of displays of related AEs, the categories 'Related', 'Possibly Related' shall be grouped together and considered as Related AEs; Unlikely/Remote will be grouped together with Not Related as 'Not related'.

Related: There is clear evidence that the event is related to the use of Study vaccine, e.g., confirmation by positive re-challenge test

Possibly Related: The event cannot be explained by the participant's medical condition, concomitant therapy, or other causes, and there is a plausible temporal relationship between the event and Study vaccine administration

Unlikely Related: An event for which an alternative explanation is more likely (e.g., concomitant medications or ongoing medical conditions) or the temporal relationship to Study vaccine administration and/or exposure suggests that a causal relationship is unlikely (For reporting purposes, Unlikely/Remote will be grouped together with Not Related)

Not Related: The event can be readily explained by the participant's underlying medical condition, concomitant therapy, or other causes, and therefore, the Investigator believes no relationship exists between the event and Study vaccine.

8.1.4 Serious Adverse Events

A serious adverse event is any adverse event that, in the view of either the Investigator or Sponsor, meets any of the following criteria:

- Results in death
- Is life-threatening, that is, poses an immediate risk of death at the time of the event. An AE or suspected adverse reaction is considered “life-threatening” if, in the view of either the Investigator or Sponsor, its occurrence places the participant at immediate risk of death. It does not include an AE or suspected AE that, had it occurred in a more severe form, might have caused death
- Requires inpatient hospitalization or prolongation of existing hospitalization.
Hospitalization is defined as an admission of greater than 24 hours to a medical facility and does not always qualify as an AE.
- Results in a persistent or significant incapacity or substantial disruption of the ability to conduct normal life functions.
- Results in a congenital anomaly or birth defect in the offspring of the participant (whether the participant is male or female).
- Important medical events that may not result in death, are not life-threatening, or do not require hospitalization may also be considered serious when, based upon appropriate medical judgment, they may jeopardize the participant and may require medical or surgical intervention to prevent one of the outcomes listed in this definition. Examples of such medical events include allergic bronchospasm requiring intensive treatment in an emergency room or at home, blood dyscrasias or convulsions that do not result in inpatient hospitalization, or the development of drug dependency or drug abuse.

All occurrences of SAE will be listed for each participant, grouped by cohort/sub-cohort. The listing will contain the following information: treatment group, verbatim term (if an unsolicited event), SOC, PT (event term if a solicited event), severity, relationship to study medication, date and day of onset, date and day of resolution, treatment given to treat the adverse event, the outcome, whether the event was an MAAE, and whether it led to withdrawal. Listings will be sorted by participant identification number, onset date, SOC, type of event (solicited or unsolicited) and PT/event term. If the onset date

is completely missing, then these events will be presented first. If the onset date is missing a month or a day, then these events will be presented before any complete dates.

Individual case narratives will be provided for all SAE.

8.1.5 Medically Attended Adverse Events (MAAE)

A MAAE is an AE that leads to an unscheduled visit (including a telemedicine visit) to a healthcare practitioner (HCP). This would include visits to a study site for unscheduled assessments (e.g., rash assessment, abnormal laboratory follow-up) and visits to or from HCPs external to the study site (e.g., urgent care, primary care physician).

All occurrences of treatment-emergent MAAEs will be listed for each participant, grouped by cohort. The listing will contain the following information: treatment group, verbatim term (if an unsolicited event), SOC, PT (event term if a solicited event), severity, relationship to study medication, date and day of onset, date and day of resolution, treatment given to treat the adverse event, the outcome, whether the event was an SAE, and whether it led to withdrawal. Listings will be sorted by participant identification number, onset date, SOC, type of event (solicited or unsolicited) and PT/event term. If the onset date is completely missing, then these events will be presented first. If the onset date is missing a month or a day, then these events will be presented before any complete dates.

Individual case narratives will be provided for all MAAEs.

8.1.6 New Onset of Chronic Disease

Any AE that includes a new diagnosis of a chronic medical condition that was not present or suspected prior to enrollment will be categorized as a new onset of chronic disease (NOCD).

All occurrences of NOCDs will be listed for each participant, grouped by cohort/sub-cohort. The listing will contain the following information: treatment group, verbatim term (if an unsolicited event), SOC, PT (event term if a solicited event), severity, relationship to study medication, date and day of onset, date and day of resolution, treatment given to treat the NOCD, the outcome, whether the NOCD was an SAE, whether it was a MAAE and whether it led to withdrawal. Listings will be sorted by participant identification number, onset date, SOC, and PT. If the onset date is completely missing, then these events will be presented first. If the onset date is missing a month or a day, then these events will be presented before any complete dates.

Individual case narratives will be provided for all NODC.

8.1.7 AE Leading to Discontinuation/Withdrawal

AE Leading to Discontinuation/Withdrawal are TEAE resulting in either discontinuation of study vaccine or withdrawal from study participation. All occurrences of AE Leading to Discontinuation/Withdrawal will be listed for each participant, grouped by cohort/sub-cohort. The listing will contain the following information: treatment group, verbatim term, SOC, PT (event term if a solicited event), severity, relationship to study medication, date and day of onset, date and day of resolution, treatment given to treat the event, the outcome, whether the event was an SAE. Listings will be sorted by participant identification number, onset date, SOC, and PT. If the onset date is

completely missing, then these events will be presented first. If the onset date is missing a month or a day, then these events will be presented before any complete dates.

Individual case narratives will be provided for all AE Leading to Discontinuation/Withdrawal.

8.1.8 Clinical Events of Special Interest

Clinical Events of Special Interest (CESI) are events relating to the detection of disease (SARS-CoV-2) activity relevant to the study vaccine. All occurrences of CESI will be listed for each participant, grouped by cohort/sub-cohort. The listing will contain the following information: treatment group, verbatim term, SOC, PT (event term if a solicited event), severity, relationship to study medication, date and day of onset, date and day of resolution, treatment given to treat the event, the outcome, whether the event was an SAE, and whether it led to withdrawal. Listings will be sorted by participant identification number, onset date, SOC, and PT. If the onset date is completely missing, then these events will be presented first. If the onset date is missing a month or a day, then these events will be presented before any complete dates.

Individual case narratives will be provided for all CESI events.

8.1.9 Adverse Event Summary:

8.1.9.1 Unsolicited Adverse Event Summaries

All unsolicited AEs (serious and non-serious) occurring after exiting Parent study and after administration of first dose of study vaccine (in this study or parent study as applicable) and before the End of Study or Off-study vaccination, regardless of relationship to study vaccine, will be included and classified by system organ class (SOC) and preferred term (PT) using the Medical Dictionary for Regulatory Activities (MedDRA).

- For Cohort 1a, AE occurring from the time of exiting the Parent Study up to receipt of Study Vaccine on Day 1 will be regarded as medical history. All unsolicited events, including SAEs, MAAEs, and NOCD are collected up to 28 days after receipt of study vaccine and only SAEs, MAAEs, and NOCD are collected beyond 28 days after receipt of study vaccine.
- For Cohort 1b, SAEs, MAAEs, and NOCD occurring from the time of exiting the Parent Study up to receipt of study vaccine on Day 1 will be regarded as treatment emergent but will be presented separately (as 'Pre-Study TEAEs') to TEAEs occurring after receipt of vaccine. All unsolicited events, including SAEs, MAAEs, and NOCD are collected up to 28 days after receipt of study vaccine in Study ARCT-021-02 but only SAEs, MAAEs, and NOCD are collected beyond 28 days after receipt of study vaccine.
- For Cohort 2 only SAEs, MAAEs, and NOCD are collected in Study ARCT-021-02 as no further study vaccine is administered in this study. All events reported from the time of exiting the Parent Study up to the data cut point for this interim analysis are regarded as treatment emergent and will be presented merged for the purposes of tabulation.

Solicited systemic and local adverse events will not be included in the unsolicited AE summaries, unless the solicited AE has onset >7 days after administration of Study vaccine or the solicited event is serious or medically attended.

Unsolicited AEs that appear within the Toxicity Grading Scale for Healthy Adult and Adolescent Volunteers Enrolled in Preventive Vaccine Clinical Trials, Sept 2007 will have been entered in the EDC with a numerical Grade (1 to 4). Unsolicited TEAEs that are not contained within this scale will have been graded as mild/moderate/severe. For the purposes of tabulation of unsolicited AEs, events will be presented as mild/moderate/severe, whereby the CRF-designated Grade 1 = mild, Grade 2 = moderate and \geq Grade 3 = severe.

For unsolicited AEs (AEs), the following will be summarized and presented at the time of final analysis for the safety and longitudinal safety population:

- i. An overall summary of TEAEs, by cohort/sub-cohort and age groups, which includes the following:
 - a. The number and percentage of participants experiencing a TEAE
 - b. The number and percentage of participants experiencing a TEAE by strongest relationship to study medication ('Related to study vaccine' vs 'Not Related'). Relationship will be determined as described in Section 8.1.3.
 - c. The number and percentage of participants experiencing a TEAE by maximal severity.
 - d. The number and percentage of participants experiencing a Related TEAE by maximal severity.
 - e. The number and percentage of participants experiencing a TEAE leading to withdrawal from study.
 - f. The number and percentage of participants experiencing a TEAE leading to death
 - g. The number and percentage of participants experiencing a treatment emergent SAE
 - h. The number and percentage of participants experiencing a treatment emergent MAAE
 - i. The number and percentage of participants experiencing NOCD
- ii. The number and percentage of participants experiencing a TEAE by SOC and PT, by age group and cohort/sub-cohort.
- iii. The number and percentage of participants experiencing a TEAE by SOC, PT and the relationship to study medication, by age group and cohort/sub-cohort.
- iv. The number and percentage of participants experiencing a related TEAE by SOC, PT and the maximal severity, by age group and cohort/sub-cohort.
- v. The number and percentage of participants experiencing a TEAE by SOC, PT, and maximal severity, by age group and cohort/sub-cohort.

The treatment emergent SAEs, MAAEs, NOCDs and AE leading to discontinuation/withdrawal will be listed.

The age groups referenced above are all participants, 21 to 55 years, and 56 to 80 years at the time of enrolment in the Parent Study. The cohort/sub-cohorts are described in Section 5.2

In the overall summary of TEAEs, Table (i), besides tabulating the number and percentage of participants, the total number of TEAE episodes will also be provided. If a participant has repeated

occurrences of a particular TEAE, all episodes will be counted in the occurrences.

In the remaining summary tables, the incidence of TEAEs will be calculated by dividing the number of participants who have experienced the event by the total number of participants in the corresponding Cohort. Thus, the incidence of TEAEs is shown in terms of the total number of participants and not in terms of the total number of episodes. If a participant has repeated episodes of a particular TEAE, only the most severe episode, or the episode with the strongest causal relationship to study vaccine, will be counted in the summary tables.

A participant with more than one type of TEAE in a particular SOC will be counted only once in the total of participants experiencing TEAEs in that particular SOC, but all PTs for that participant will be shown. Since a participant could have more than one type of TEAE within a particular SOC, the sum of participants experiencing different TEAEs within the SOC could appear larger than the total number of participants experiencing TEAEs in that SOC. Similarly, a participant who has experienced a TEAE in more than one SOC will be counted only once in the total number of participants experiencing AEs in all SOCs.

All occurrences of all TEAEs will be listed for each participant, grouped by cohort. The listing will contain the following information: treatment group, verbatim term, SOC, PT, severity, relationship to study medication, date and day of onset, date and day of resolution, treatment given to treat the adverse event, the outcome, whether the event was an SAE and/or a MAAE and/or NOCD, and whether it led to withdrawal. Listings will be sorted by participant identification number, onset date, SOC, and PT. If the onset date is completely missing, then these events will be presented first. If the onset date is missing a month or a day, then these events will be presented before any complete dates.

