10.5.3 Safety Analysis

The primary objective of the study is the evaluation of the safety and tolerability of ARCT-021. The primary endpoints that align with this objective are:

- Solicited AEs for 7 days after vaccination (Cohort 1), summarized by toxicity grade
- Unsolicited AEs for 28 days after vaccination (Cohort 1), summarized by mild/moderate/severe and relationship to ARCT-021
- SAEs through Day 197 (Cohort 2; 12 months after ARCT-021 vaccination in ARCT-021-01 study), summarized by relationship to ARCT-021
- SAEs through Day 365 (Cohort 1; 12 months after ARCT-021 vaccination in ARCT-021-02 study), summarized by relationship to ARCT-021
- MAAEs through Day 197 (Cohort 2; 12 months after ARCT-021 vaccination in ARCT-021-01 study), summarized by relationship to ARCT-021
- MAAEs through Day 365 (Cohort 1; 12 months after ARCT-021 vaccination in ARCT-021-02 study), summarized by relationship to ARCT-021
- NOCDs through Day 197 (Cohort 2; 12 months after ARCT-021 vaccination in ARCT-021-01 study), summarized by relationship to ARCT-021
- NOCDs through Day 365 (Cohort 1; 12 months after ARCT-021 vaccination in ARCT-021-02 study), summarized by relationship to ARCT-021
- Safety laboratory assessments through 28 days after vaccination (Cohort 1), summarized by toxicity grade (where relevant)

- Vital signs assessments through day 365 (Cohort 1; 12 months after ARCT-021 vaccination in ARCT-021-02 study) summarized by toxicity grade

To support the continued characterization of ARCT-021 tolerability and safety when administered as a single dose, the following summaries will be provided:

- Summary of solicited (7 days after vaccination) and unsolicited AEs 28 days after vaccination)
- Summary of MAAEs, NOCDs, SAEs through 12 months after vaccination

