8. SAFETY ANALYSIS

The primary objective of the study is the evaluation of the safety of ARCT-021. The primary endpoints that align with this objective are:

- Solicited AEs for 7 days after vaccination with ARCT-021 (Cohort 1 only).
- Unsolicited AEs within 28 days after vaccination with ARCT-021 (Cohort 1 only), summarized by mild/moderate/severe and relationship to ARCT-021.
- SAEs, MAAEs, NOCD and AE leading to discontinuation/withdrawal according to the following windows
 - Pre-Study for cohort 1b
 - Within 28 days after vaccination with ARCT-021 (Cohort 1 only)
 - from 28 days after vaccination to the last observation prior to receipt of off study vaccine or prior the data cut point for this interim, whichever is first (all cohorts/sub-cohorts).
- Safety laboratory assessments through 28 days after vaccination with ARCT-021 (Cohort 1 only), summarized by toxicity grade (where relevant).
- Vital signs assessments through the last observation prior to receipt of off study vaccine or prior to the data cut point for this interim, whichever is first, summarized by toxicity grade.
- Unsolicited AEs, MAAEs, SAEs and vital signs assessments from after receipt of off-study vaccine up to the observation prior to the data cut point for this interim.

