8.1.1 Treatment-emergent Adverse Events

All adverse events that start on or after study vaccine administration are classified as treatment emergent adverse events (TEAEs).

- For Cohort 1a, treatment emergent events are those arising after receipt of ARCT-021 on Day 1 in Study ARCT-021-02
- For Cohort 1b and Cohort 2, treatment emergent events comprise any events occurring since the participant exited the Parent Study

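### The unsolicited TEAE tables in SAP 8.1.9.1 carry no 28-day onset limit, so as specified they do not give the primary unsolicited-AE endpoint, and their any-TEAE rows are not comparable between Cohorts 1 and 2

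*SAP*

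**What the plan says.** **Endpoint.** SAP Section 8 lists among the primary endpoints "Unsolicited AEs within 28 days after vaccination with ARCT-021 (Cohort 1 only), summarized by mild/moderate/severe and relationship to ARCT-021". Protocol 10.5.3 says the same: "Unsolicited AEs for 28 days after vaccination (Cohort 1), summarized by mild/moderate/severe and relationship to ARCT-021". SAP 8.1 adds that all AEs are reported for Cohort 1 up to 28 days after injection.

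**Tables.** SAP 8.1.9.1 admits to the unsolicited summaries every event after Parent Study exit and first dose, and "before the End of Study or Off-study vaccination, regardless of relationship to study vaccine, will be included". Tables i to v then summarise TEAEs by cohort/sub-cohort and age group. The first line of table i is "The number and percentage of participants experiencing a TEAE"; lines by relationship and maximal severity follow. The tables "will be summarized and presented at the time of final analysis for the safety and longitudinal safety population". No table in the list states an onset window. Outside the table i overview, which also counts episodes, incidence is participants with the event divided by participants in the cohort, with no allowance for exposure.

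**Collection.** The same section states that for Cohorts 1a and 1b "only SAEs, MAAEs, and NOCD are collected beyond 28 days after receipt of study vaccine", and "For Cohort 2 only SAEs, MAAEs, and NOCD are collected in Study ARCT-021-02". SAP 8.1.1 sets the clock: "For Cohort 1b and Cohort 2, treatment emergent events comprise any events occurring since the participant exited the Parent Study". Cohort 1b events before Day 1 are shown separately. Cohort 2 events since Parent Study exit are merged.

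**The concern.** The endpoint and the tables that should report it follow different rules. A programmer working from 8.1.9.1 would count every eligible event up to end of study or off-study vaccination. The resulting Cohort 1 percentage is not the 28-day rate and grows with each later data cut. Tables i to v are also the only planned summaries of unsolicited AEs before off-study vaccination that give severity and relationship; SAP 8.1.4 to 8.1.8 specify listings and narratives.

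The rows also change meaning between cohorts. For Cohort 1, an any-TEAE row contains all unsolicited AEs for 28 days and selected categories afterwards. For Cohort 2, it contains the selected categories throughout, on a clock that starts before Day 1 of this study. A difference between the two columns can arise with no difference in risk.

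Safety is the primary objective, and SAP Section 4 says this interim supports a regulatory filing. What is at stake is how descriptive safety rates are read.

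**Working it through.** The documents state no event rate or expected percentage for these rows, so there is no plan figure to reproduce. The textual check comes first, then an illustration.

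**Text side by side**

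| Item | Endpoint (SAP 8, protocol 10.5.3) | Tables i to v (SAP 8.1.9.1) |
|---|---|---|
| Onset window | 28 days after vaccination | To end of study or off-study vaccination |
| Participants | Cohort 1 | Safety Population (Cohort 1) and Longitudinal Safety Population (adds Cohort 2) |
| Events possible after Day 28, Cohort 1 | None | SAE, MAAE, NOCD |
| Events possible, Cohort 2 | Not applicable | SAE, MAAE, NOCD only |

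**Inputs for the illustration**
- Cohort 1 final visit at Day 365, which is 364 days after dosing; Day 57 is 56 days after dosing (protocol 3.8.3).
- Cohort 2: a nominal 90 days from Parent Study exit to Day 1 (SAP 5.3.2). Day 29 is then 90 + 28 = 118 days after exit, and the final visit on Day 281 is 90 + 280 = 370 days after exit.
- Assumed, not in the documents: 28-day risk of any unsolicited AE p = 20% to 40% (central 30%); 28-day risk of an SAE, MAAE or NOCD m = 1% to 5% (central 3%); constant rates, the same true risk in both cohorts, no censoring at off-study vaccination.

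**Formulas**
- Cohort 1, d days after dosing (d at least 28): 1 − (1 − p)(1 − m)^((d − 28)/28)
- Cohort 2, d days after Parent Study exit: 1 − (1 − m)^(d/28)

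**Central case (p = 0.30, m = 0.03)**
- Cohort 1, 28 days: 30.0%
- Cohort 1, Day 57: 1 − 0.70 × 0.97 = 32.1%
- Cohort 1, Day 365: 1 − 0.70 × 0.97^12 = 1 − 0.70 × 0.694 = 51.4%
- Cohort 2, Day 29: 1 − 0.97^(118/28) = 1 − 0.880 = 12.0%
- Cohort 2, Day 281: 1 − 0.97^(370/28) = 1 − 0.669 = 33.1%

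Over a common 28 days the two cohorts would show 30.0% and 3.0%. That gap comes wholly from what is collected.

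**Range over the assumed grid**

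| Row value | Lowest | Highest |
|---|---|---|
| Cohort 1, 28-day window | 20% | 40% |
| Cohort 1, by Day 365 | 29.1% | 67.6% |
| Cohort 2, by Day 29 | 4.1% | 19.4% |
| Cohort 2, by Day 281 | 12.4% | 49.2% |

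With the 28-day limit applied, the Cohort 1 figure equals p whatever the follow-up.

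**The case against.** The case for leaving the plan alone has several sound parts.

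- **The window is in the SAP.** Section 8 keeps it, and 8.1 refers to 28 days. A reader might infer that the SAP has abandoned the primary endpoint. The text does not support that: it is an inconsistency between the endpoint and the table list. The table shells are not in the documents, so a window could appear there. Even so, 8.1.9.1 states a positive inclusion rule that gives a different number, and the sentence in 8.1 is never turned into an onset limit for the tables.
- **The 28-day rate is recoverable.** The TEAE listing carries day of onset, severity, relationship and SAE/MAAE/NOCD flags. This stands, and it is why the fix is cheap. A listing is still not a planned summary of a primary endpoint.
- **Cohort 2 is kept apart.** The Safety Population excludes it (SAP 5.2), rows are by cohort/sub-cohort, and the collection difference is disclosed. A reader might infer a pooled total mixing Cohorts 1 and 2; none is specified. The SAE, MAAE and NOCD rows collect the same event types in every cohort. What remains is that the any-TEAE, relationship and severity rows bear one label with two meanings.
- **The protocol wants an all-TEAE summary.** The synopsis (Statistical Considerations) calls for incidence of all TEAEs by system organ class and preferred term, and by relationship, seriousness and severity. This stands: cutting tables i to v down to 28 days would remove it, so the 28-day version should be an addition.
- **The analyses are descriptive, and the rates above are assumed.** Both are true. Off-study vaccination occurred in many instances (SAP 5.3.3), and censoring there would pull the late figures down. At Day 57 the central case moves only from 30.0% to 32.1%.

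**Conclusion.** The point holds as an inconsistency between the primary endpoint and its table specification. Followed as written, 8.1.9.1 yields a full-period Cohort 1 percentage instead of the 28-day rate, and places Cohort 2 under row labels that mean something narrower there. The direction for Cohort 1 is certain: the full-period figure cannot be below the 28-day figure. The size is not known. It rests on the assumed rates, equal true risk and absence of censoring stated above, and is small at an early cut and larger near Day 365.

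A reader might go further and take a lower Cohort 2 percentage as planned evidence of better safety. The SAP plans no formal hypothesis testing and says what Cohort 2 collects, so it makes no such claim; the risk lies in how the rows are read. A 28-day table would also be the cleaner one: SAP 8.1.9.3 reports that no participant received an off-study vaccine while all unsolicited AEs were being collected, so that censoring does not touch it.

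This is a should-fix, not a must-fix.

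**What to change.** 1. Add to SAP 8.1.9.1 a version of tables i to v for the Safety Population (Cohorts 1a and 1b), limited to onset from dosing through 28 days after dosing, and designate it the primary unsolicited-AE analysis. Keep the full-period all-TEAE tables as supportive.
2. Tabulate SAEs, MAAEs and NOCDs for all cohorts by the Section 8 windows, with relationship. Protocol 10.5.3 asks for relationship for each of these, and table i gives only their counts and percentages.
3. In the Longitudinal Safety tables, retitle the Cohort 2 any-TEAE, relationship and severity rows as any SAE/MAAE/NOCD.

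SAP 5.1 rules out changes once the interim data are pulled. If that has happened, issue these as documented supplementary tables and apply them in the final analysis. The cost is SAP wording, table shells and programming. No new data are needed.

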3.8.3 Post Treatment

Subjects who are not receiving ARCT-021 in this study

Subjects will have visits on Day 1, Day 29, Day 85, Day 197 and Day 281. The Final visit will be on Day 281.

Subjects receiving a single injection of ARCT-021

Subjects will return for outpatient visits on Days 8, 15, 29, 57, 169, 253 and 365. The final visit will be on Day 365.

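### Long-term SAE, MAAE and NOCD percentages stop counting at off-study vaccination or data cut but report no time at risk, so they depend on uptake and cut date and cannot be compared between cohorts

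*SAP*

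**What the plan says.** **Where counting stops.** SAP 5.3.3 records that many participants received a COVID-19 vaccine outside the study and censors their data from then on. SAP 3.1 and 5.4 apply this to safety reports at the first off-study dose. The lead sentence of SAP 8.1.9.1 says that unsolicited events occurring "before the End of Study or Off-study vaccination, regardless of relationship to study vaccine, will be included". SAP 8 ends the beyond-28-day window for SAEs, MAAEs and NOCDs at the earlier of off-study vaccine and interim data cut, for every cohort and sub-cohort.

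**What the counts are divided by.** Tables ii to v of SAP 8.1.9.1 obtain incidence by "dividing the number of participants who have experienced the event by the total number of participants in the corresponding Cohort". Table (i) holds the overall SAE, MAAE and NOCD rows, for example "The number and percentage of participants experiencing a treatment emergent MAAE", and names no denominator. SAP 8.1.9.3 tabulates events after off-study vaccine in the Longitudinal Safety Population by age group, also without a stated denominator.

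**Where counting starts.** Cohort 1a starts at Day 1 of this study. Cohort 1b events before Day 1 are shown separately. Cohort 2 starts at exit from the Parent Study, nominally 90 days before Day 1 (SAP 4.4, 5.3.2, 8.1.1).

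**What the protocol specified.** Protocol 10.5.3 has fixed windows: "MAAEs through Day 365 (Cohort 1; 12 months after ARCT-021 vaccination in ARCT-021-02 study), summarized by relationship to ARCT-021" and "MAAEs through Day 197 (Cohort 2; 12 months after ARCT-021 vaccination in ARCT-021-01 study), summarized by relationship to ARCT-021", with the same pattern for SAEs and NOCDs.

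**What is absent.** Neither document provides for follow-up duration, number at risk, person-time or number censored by cohort. A Censoring Day is defined in SAP 5.3.3, but no table summarises it.

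**The concern.** The numerator is cut at a different time for each participant, while the only stated denominator counts every cohort member in full. Someone censored early weighs as much as someone followed to the end.

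Stopping can also differ by cohort. In Protocol 5.2 the exclusion for other SARS-CoV-2 vaccines applies only to subjects who will be dosed in this study, so it does not cover Cohort 2. SAP 5.3.3 provides for off-study doses before enrolment. A Cohort 2 participant may therefore contribute no uncensored in-study time and still count in the denominator.

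Long-term SAEs, MAAEs and NOCDs are primary safety endpoints (Protocol 10.5.3, SAP 8), and the tables are laid out by cohort and sub-cohort. Without time at risk, a reader cannot tell whether a lower percentage means fewer events or less time counted.

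**Working it through.** The plan states no expected safety percentage, so there is no figure to reproduce. Uptake, its timing, the cut date and event rates are not given. Everything below is illustration. Steps 1 to 4 assume a constant hazard and, where uptake enters, non-informative censoring.

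**1. Uptake, Cohort 1.** Assume a true risk of 20% over the 364 days from Day 1 to Day 365. Then h = −ln(0.80)/364 = 0.000613 per day. Let off-study vaccination be uniform over days 28 to 364 after dosing (SAP 8.1.9.3 says none fell in the 28-day window). Mean counted risk in those vaccinated is 1 − (e^(−28h) − e^(−364h))/(336h) = 0.1116. With uptake p, the crude percentage is (1 − p) × 0.20 + p × 0.1116:

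| Uptake | 0% | 25% | 50% | 75% |
|---|---|---|---|---|
| Shown | 20.0% | 17.8% | 15.6% | 13.4% |

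Two groups with equal risk but 25% and 75% uptake differ by a ratio of 13.4/17.8 = 0.75. For true risks of 5% and 30%, the figures at 75% uptake are 3.3% and 20.3%, or 0.66 and 0.68 of the true value.

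**2. Data cut.** Same h, no uptake. Follow-up to Day 57 shows 1 − e^(−56h) = 3.4%. To Day 169 it shows 1 − e^(−168h) = 9.8%.

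**3. Starting point.** In the single-dose cohorts, parent exit (Day 57) is 56 days after dosing, and SAP 5.3.2 puts Day 1 of this study at 147 days, a gap of 91 days. At a Day 57 cut with no uptake, Cohort 1a has 56 days counted and Cohort 2 has 91 + 56 = 147. At the same h these show 3.4% and 1 − e^(−147h) = 8.6%.

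**4. Direction in Cohort 2 (A to D2).** Use the protocol's Day 197 point only as a yardstick. Protocol 3.8.3 says of subjects not dosed here: "The Final visit will be on Day 281". Day 197 is 147 + 196 = 343 days after dosing and Day 281 is 147 + 280 = 427. From parent exit the windows are 343 − 56 = 287 and 427 − 56 = 371 days. With 20% risk over 287 days, h = −ln(0.80)/287 = 0.000778, and full follow-up to Day 281 shows 1 − e^(−371h) = 25.1%. With off-study vaccination uniform over the window, mean counted risk in those vaccinated is 13.1%, and the crude figures are 25.1%, 22.1%, 19.1% and 16.1% at 0%, 25%, 50% and 75% uptake. They cross 20% at p = (0.2506 − 0.2000)/(0.2506 − 0.1313) = 0.42. The crossing moves to 0.23 if all off-study doses precede Day 1, and to 0.58 if all follow it. The sign is therefore not fixed.

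**5. SAP 8.1.9.3.** If the whole population were the denominator, a 10% risk in recipients would show as 2.5%, 5.0% and 7.5% at 25%, 50% and 75% uptake (0.10 × p).

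**6. Does person-time cure it?** Under the constant hazard of step 1 the rate is 0.000613 × 365.25 × 100 = 22.4 per 100 person-years at any uptake, but this only restates the assumption. Suppose instead a hazard of 1.0 per year for 28 days (a per day) and 0.15 per year afterwards (b per day). First events per person to day T are 1 − e^(−28a)e^(−b(T−28)). Time at risk is (1 − e^(−28a))/a + e^(−28a)(1 − e^(−b(T−28)))/b:

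| Followed to | Events per person | Days at risk | Per 100 person-years |
|---|---|---|---|
| Day 57 | 0.0844 | 52.7 | 58 |
| Day 169 | 0.1255 | 153.0 | 30 |
| Day 365 | 0.1932 | 317.6 | 22 |

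Cohort 2, counted only after parent exit, shows 15. A single rate pooled from Day 1 still depends on cohort and data cut. Splitting at Day 28 removes this here, because the later hazard is 15 per 100 person-years in both.

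**The case against.** The strongest case against is about consequence. The analysis is descriptive, with no testing. At most 106 participants (SAP 3.1) are spread over 15 sub-cohorts. Every SAE, MAAE and NOCD is listed with onset day and given a narrative (SAP 8.1.4 to 8.1.6). Column counts may appear in table shells we do not have. Protocol 10.5.2 plans disposition summaries, and SAP 6.4 tabulates concomitant medications including vaccines for the Safety Population. All of this limits the harm, but none of it relates events to time at risk. With no model planned, the percentages are what readers will use.

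A reader might infer more than the documents support:

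- **That SAP 8.1.9.1 contradicts itself.** Its Cohort 2 bullet speaks of "All events reported from the time of exiting the Parent Study up to the data cut point for this interim analysis" without repeating the off-study stop. The section's lead sentence and the all-cohorts window in SAP 8 already apply that stop, and SAP 8.1 repeats the split, so this is not a conflict.
- **That the SAP misstates 12-month risk.** Day 365 and Day 197 are protocol endpoints. The interim SAP does not claim that its percentages estimate them.
- **That the figures flatter the vaccine.** Step 4 shows that the Cohort 2 direction is open.
- **That events are lost.** Those after off-study vaccine are tabulated separately in SAP 8.1.9.3.
- **That the quoted denominator governs every row.** It covers tables ii to v. For Table (i) the point is that none is stated.

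**Conclusion.** The concern holds as a reporting gap that should be closed. As written, the SAP yields long-term SAE, MAAE and NOCD percentages that vary with off-study uptake, data cut and starting point, and nothing reported allows a reader to adjust for this. The actual size cannot be derived, nor can the direction for Cohort 2. The illustrations show that, with equal true rates, a ratio of 0.75 between two Cohort 1 groups is possible from uptake alone. They rest on assumed risk, uptake and timing, a constant hazard and non-informative censoring; informative censoring could change size or sign. The 28-day Cohort 1 window is unaffected, because SAP 8.1.9.3 states that no off-study vaccination fell within it.

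**What to change.** Keep the counts and percentages. For the main cohorts 1a, 1b and 2 only:

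- Add the number censored at off-study vaccine, median follow-up and person-time.
- Add first-event SAE, MAAE and NOCD rates per 100 person-years with exact confidence intervals. End person-time at off-study vaccine, withdrawal or data cut.
- Report Cohort 1 rates separately for Days 1 to 28 and after Day 28, the windows SAP 8 already uses. Compare only the after-Day-28 rate with Cohort 2.
- Label the Cohort 2 window by its actual start (parent-study exit) and end.
- State the Table (i) denominator.
- In SAP 8.1.9.3, use off-study-vaccine recipients and their time after that vaccine.

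SAP 5.1 allows no change after the data pull. If that has passed, the text belongs in the plan for the final analysis, since SAP 8.1.9.1 says "the following will be summarized and presented at the time of final analysis for the safety and longitudinal safety population".

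The cost is a short paragraph and a few columns; the off-study vaccine date and onset day are already needed for Censoring Day and the listings. The rates will be imprecise: 5 first events in an assumed 30 person-years give 16.7 per 100 person-years, exact 95% CI 5.4 to 38.9. Person-time does not correct informative censoring, or the retrospective collection at screening of events between the two studies.
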